#### 2.2.5.5 Device Malfunction

Percent of patients with suspected HM3 device malfunctions and frequency of all suspected malfunctions will be reported by components of HM3 involved. Additionally, days to the malfunction, reoperations or death due to malfunction and actions taken in response to malfunction will be reported.

### 2.3 Sample Size Calculations

No formal sample size calculation is required. Sample size is based on the estimated number of consecutive patients likely to be implanted with a HM3 at the participating sites during the study period.

*This confidential document is the property of Abbott and shall not be reproduced, distributed, disclosed or used without the express written consent of Abbott.*

## Statistical Analysis Plan

### 2.4 Interim Analysis

No formal interim analyses are planned for this study. As such, no formal statistical rule for early termination of the trial is defined. Interim study reports with descriptive analysis may be produced for regulatory or reimbursement purposes.

### 2.5 Timing of Analysis

All endpoints will be analyzed at the end of the 2-year surveillance period.

### 2.6 Study/Trial Success

There is no formal definition of success in this PMS.

### 2.7 Subgroups for Analysis

No subgroup analyses are planned for this PMS.

### 2.8 Handling of Missing Data

Data collected outside of the study visit window will be excluded from the analysis. Except for 6-minute Walk Test stated above, missing data will not be imputed.

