6.3 Follow-Up Visit Assessments

The assessments listed in **Table 3** will be performed at all other visits (i.e. at 1, 3, 6, 12 and 24 months) post HM3 Implant, unless the subject experiences an outcome; for the purposes of this PMS a month is defined as 30 days. The required assessments, follow-up schedule, and associated visit windows (**Table 4**) are generally aligned with SOC LVAD patient follow up. All follow-up visits are based on the HM3 implant date.

Table 3. Follow-up visit assessments.

Study Activity	Definition
Subject Status	Whether the subject is on HM3 LVAD support, if not, what was the outcome the patient experienced (i.e. death, transplant, withdrawn, pump exchange or explant)
Vital Signs	Weight, blood pressure and method of blood pressure measurement, and heart rate
Pump Parameters	Pump speed, flow, power and pulsatility index
Medications	Inotropes, anticoagulation/antiplatelet (Aspirin, Persantine, Plavix, warfarin, Other), antibiotics, vasodilators, diuretics, anti-arrhythmic, ACEi, ARB and beta blockers.
Laboratory Assessments	Hemoglobin, hematocrit, white blood cell count, platelets, creatinine, estimated glomerular filtration rate, liver function tests (AST, ALT, total bilirubin, albumin, pre-albumin), blood urea nitrogen, INR, LDH.
Echocardiogram ¹	LVEF, LVEDD, LVESD, AI, MR, TR, PR, including new onset, severity and/or grade, and presence of LV or LA thrombus, and aortic valve opening ratio
Functional Capacity	6-minute Walk Test and NYHA Class
Quality of Life	EQ-5D-5L quality of life questionnaire

¹If collected per SOC.

The follow-up visit must occur within the designated window (**Table 4**). The assessments for a single visit do not have to occur on the same date, but must occur within the designated window, or will be considered a protocol deviation. The Sponsor understands that some lab results may be received several days after the visit has occurred, in these instances the date

This confidential document is the property of Abbott and shall not be reproduced, distributed, disclosed or used without the express written consent of Abbott

Post Market Surveillance Plan

the blood draw occurred will be considered as the date of the lab assessment. All subjects should be asked, at each follow up visit, if they were seen at an outside facility. If so, medical records from any facility that has seen the patient must, with the subject's consent, be requested and reviewed for potential adverse events.

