Table 4. Follow-up visit windows.

Visit 0	Visit 1	Visit 2	Visit 3	Visit 4	Visit 5	Visit 6
Baseline/ Enrollment	Implant	Month 1 ± 7 days	Month 3 ± 30 days	Month 6 ± 30 days	Month 12 ± 30 days	Month 24 ± 60 days
Patients will be followed until the 24 months visit or they experience an outcome.						

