### 1.4 Endpoints

#### 1.4.1 Primary Efficacy Endpoint

Primary efficacy endpoint is defined as the overall survival to transplant, myocardial recovery or on device support free of debilitating stroke (Day 60 Modified Rankin Score >3) or reoperation for pump replacement during the 24 months surveillance period. Subjects who are urgently transplanted due to a HM 3 malfunction prior to 24 months will be considered to have experienced a primary endpoint event, as will subjects who expire, suffer a debilitating stroke or have their HM3 exchanged due to a device failure prior to 24 months.

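### Excluding every value taken outside a visit window drops real walk-test, NYHA and EQ-5D-5L measurements, and the sentence does not say which data it covers

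*SAP*

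**What the plan says.** SAP 2.8 sets the rule: "Data collected outside of the study visit window will be excluded from the analysis". Protocol 8.6 carries the same sentence. Neither names the data it applies to or exempts any. Both then rule out imputation, except that a subject unable to walk because of heart failure scores 0 metres. Protocol 8.2.3.1 leaves 6MWT values missing for any other reason out of the analysis.

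The windows are in protocol Table 4, counted from implant, and protocol 6.3 adds that "for the purposes of this PMS a month is defined as 30 days". Month 1 has ±7 days. The others are "Month 3 ± 30 days", "Month 6 ± 30 days", "Month 12 ± 30 days" and "Month 24 ± 60 days". Protocol 6.3 classes an assessment outside its window as a protocol deviation.

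Protocol Table 5 also allows functional capacity and EQ-5D-5L at unscheduled visits if done as standard of care. Adverse events, outcomes, rehospitalizations, reoperations, device deficiencies and the Modified Rankin Score appear only in its as-occurs or unscheduled column.

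6MWT and EQ-5D-5L are compared with baseline at each visit by the Wilcoxon signed-rank test, and NYHA class by McNemar's test (SAP 2.2.5.1 to 2.2.5.3).

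**The concern.** A paired test uses only subjects with both a baseline and a follow-up value. Once a late measurement is excluded and not imputed, the subject drops out of that visit's comparison although the measurement exists. With about 30 subjects enrolled and fewer on support later, each lost pair costs precision. If lateness is related to health, the subjects who remain may also be unrepresentative.

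The second matter is scope. The primary efficacy endpoint is a 24-month Kaplan-Meier analysis. The primary safety endpoint is the percentage of subjects with events and events per patient-year over the surveillance period. Both need events on every day of follow-up, and a blanket exclusion tied to visit windows does not fit them. A programmer should not have to guess which data the sentence covers.

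**Working it through.** The plan gives no figure of its own to reproduce: the sample size is an enrolment estimate and the endpoints are not powered (SAP 1.4 and 2.3).

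**Windows in days after implant** (nominal day = 30 × month)

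| Visit | Nominal day | Window | Days covered |
|---|---|---|---|
| Month 1 | 30 | 23–37 | 15 |
| Month 3 | 90 | 60–120 | 61 |
| Month 6 | 180 | 150–210 | 61 |
| Month 12 | 360 | 330–390 | 61 |
| Month 24 | 720 | 660–780 | 121 |

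**What the rule does to a functional value.** A Month 1 walk test on Day 40 is 40 − 37 = 3 days past its window and 20 days before the Month 3 window opens, so it counts nowhere. It is 10 days from nominal, or 10/30 = 33% of the elapsed time. A Month 3 test on Day 120 is 30/90 = 33% from nominal and is kept. An unscheduled value between windows is likewise unusable. That matters to the paired test only when the scheduled value is missing.

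**Size of the loss.** The documents give no out-of-window rate. Assume 5% to 30%, with all 30 subjects attending all 5 visits (30 × 5 = 150 subject-visits):

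- Values lost: 150 × 0.05 = 7.5 to 150 × 0.30 = 45.
- Pairs left per visit: 30 × 0.95 = 28.5 to 30 × 0.70 = 21.
- Approximate widening of the standard error of a mean change: √(30/28.5) = 1.03 to √(30/21) = 1.20.

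This range illustrates the assumption and does not estimate the loss. Wide windows after Month 1 favour the low end.

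**Scope, on the literal reading only.** The windows cover 15 + 61 + 61 + 61 + 121 = 319 of Days 1–780. The gaps (Days 1–22, 38–59, 121–149, 211–329 and 391–659) total 22 + 22 + 29 + 119 + 269 = 461 days. That is 461/780 = 59%, or 461/720 = 64% of the days to nominal Month 24.

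The SAP's primary endpoint uses "debilitating stroke (Day 60 Modified Rankin Score >3"), a score with no scheduled visit. Assume Day 60 is counted from stroke onset, which the SAP does not say. For onset on Days 1–660, the score date then falls in a window for 60 + 61 + 61 + 61 = 243 onset days and in none for 660 − 243 = 417 (63%).

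These counts show how far the literal sentence departs from the endpoint definitions. They say nothing about how much functional data would be lost.

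**Nearest-visit assignment without a cap.** Month 12 would run from the midpoint (180 + 360)/2 = Day 270 to (360 + 720)/2 = Day 540, against Days 330–390 now. A Day 535 test would count as Month 12 although 535 − 360 = 175 days late. Any reassignment therefore needs a cap.

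**The case against.** The strongest reply is that the rule is narrower than it looks. Windows exist only for scheduled follow-up visits, and protocol 6.3 ties them to visit assessments. Adverse events are collected as they occur (protocol 6.4.1) and throughout follow-up (protocol 7.3.1). The primary endpoint has its own censoring rule (SAP 2.2.3). Table 4 gives baseline and implant no window, so a literal reading would delete the baseline data too, which cannot be meant. This largely stands. A reader might infer that the plan will discard deaths, strokes and adverse events on most follow-up days. The documents do not support that, and the 59% and 64% figures describe only a reading that the rest of the plan contradicts. What remains is a sentence without a stated scope.

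A reader might also infer that late visits are those of sicker subjects, so that the rule flatters the device. Protocol 6.4.3 weakens this, because visit assessments continue on schedule during hospitalization. SAP 3.3 provides for reporting endpoints affected by COVID-19 but does not say that disruption is expected. Bias remains possible and is not demonstrated.

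Finally, in-window analysis is pre-specified consistently in both documents, the endpoints are unpowered and there is no success criterion (SAP 2.6). That lowers the stakes. It does not explain why valid measurements should be discarded when the deviation is already recorded and the SAP body contains no sensitivity analysis.

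**Conclusion.** The point holds as a modest analysis defect with a wording gap attached. Out-of-window 6MWT, NYHA and EQ-5D-5L values are lost from the paired comparisons in a cohort of about 30, with no imputation and no alternative analysis. The amount is unknown. Under an assumed 5% to 30% out-of-window rate with full attendance, 21 to 28.5 of 30 pairs would remain per visit, and the wide later windows make a small loss plausible.

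The missing scope limit puts the literal sentence in conflict with the whole-period primary and safety endpoints. It needs clarifying, but it is not evidence that events would be dropped in practice.

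**What to change.** Change the sentence in SAP 2.8 and protocol 8.6 together:

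- Limit the window rule to by-visit summaries of scheduled assessments.
- State that outcomes, adverse events, Modified Rankin Scores, reoperations, rehospitalizations and device malfunctions are analysed whatever their date.
- Assign out-of-window 6MWT, NYHA and EQ-5D-5L values to the nearest visit within pre-specified, capped analysis windows. If several values fall in one window, use the one closest to the nominal day.
- Report this analysis beside the in-window-only analysis.

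The visit windows in Table 4 stay as they are, and out-of-window visits remain protocol deviations. No new data collection is needed. The cost is wording in two documents, one additional table, and more spread in actual assessment time within a nominal visit, which the caps limit.

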### 2.9 Poolability Issue

The objective of this PMS is to assess real-world clinical and functional outcomes under Hong Kong and Taiwan standard of care for advanced heart failure patients implanted with the HM3 LVAS. Therefore, data from all sites will be used in the analysis.

### 2.10 Multiplicity Issues

No adjustments for multiplicity will be made.

### 2.11 Adjustments for Covariates

Unless otherwise specified, no adjustments for covariates will be made for any of the variables in the analyses.

### 2.12 Exploratory Analysis

No exploratory analysis is planned for this study.

## 3.0 DESCRIPTIVE ENDPOINTS AND ADDITIONAL DATA

### 3.1 Baseline and Demographic Characteristics

Baseline demographic variable will be summarized for subjects enrolled, including but not limited to age, gender, ethnicity, cardiovascular disease history, medical history, vital signs, echocardiogram, medications and laboratory assessments.

*This confidential document is the property of Abbott and shall not be reproduced, distributed, disclosed or used without the express written consent of Abbott.*

## Statistical Analysis Plan

### 3.2 Protocol Deviation

Protocol deviations will be summarized by major and minor categories for subjects in whom a protocol deviation was reported.

### 3.3 COVID-19

Any primary and secondary endpoints or additional data affected by or related to COVID-19 will be reported.

## 4.0 DOCUMENTATION AND OTHER CONSIDERATIONS

All analyses will be performed using SAS® for Windows, version 9.2 or higher.

## 5.0 ACRONYMS AND ABBREVIATIONS

Acronym or Abbreviation	Complete Phrase or Definition
BMI	Body Mass Index
CIP	Clinical Investigation Plan
EPPY	Event Per Patient-Year
EQ-5D-5L QoL	EuroQoL-5D-5L Quality of Life
GI	Gastrointestinal
HM3	HeartMate 3™
LVAS	Left Ventricular Assist System
NYHA	New York Heart Association
PMS	Post-Market Surveillance
AE	Adverse Event
SAP	Statistical Analysis Plan
VAS	Visual Analog Scale
6MWT	Six Minute Walk Test

*This confidential document is the property of Abbott and shall not be reproduced, distributed, disclosed or used without the express written consent of Abbott.*

### 7.0 APPENDICES

N/A
